2.1.3 Secondary Objective

• To determine the effectiveness of IMPACT by format of intervention (in-person vs. virtual)

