2.2.3 Secondary Endpoints

- Distinct acts of CAS by intervention format
- Stimulant use by intervention format

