2.2.4 Non-Clinical Implementation Endpoints

- Adoption and Accessibility*
 - Intervention uptake and completion rates by participant demographics, intervention format, site characteristics, and interventionist background
 - Client Satisfaction Questionnaire (CSQ)-8 scale scores and intervention satisfaction rates
 - *Satisfaction* is defined a priori by achieving standardized scores of 80 percent or greater on the CSQ-8 scale.^[74]

*The following implementation measures are approved as an exempt component of this research: interventionist knowledge, self-efficacy, and skills pre- and post-training, by format, site, and timepoint

- Maintenance
 - Structured qualitative interview of individuals responsible for conducting the IMPACT intervention at each site
 - Coding of a select subset of participant and staff qualitative interview transcripts to identify themes related to intervention implementation and dissemination
 - Incremental cost-effectiveness of IMPACT versus eSOC estimated using the Cost Effectiveness of Preventing AIDS Complications for Adolescents and Young Adults (CEPAC-AYA) model

3. Study Design

We will use the RE-AIM Framework to inform the design, implementation, and evaluation of the IMPACT intervention to reduce stimulant use and concurrent HIV sexual transmission risk. Following best practices described in the Expert Recommendations for Implementing Change (ERIC) framework,^[17] we will use a multifaceted training and implementation strategy for the Project IMPACT intervention across sites and formats (see details below). We will then enroll approximately 450 YGBSMM who report stimulant use in the context of CAS, who will be randomized using a 2:1 allocation ratio to either the IMPACT intervention or an eSOC control. Allowing for drop out prior to randomization, we aim to randomize 360 YGBSMM. To ensure geographic variability in our sample, we will enroll nationally. Those physically located near a participate in-person, while those not located near an ATN SC will participate virtually (i.e., online assessments and video-based counseling). We anticipate that about 50 percent of the randomized sample will participate virtually (n=180) and 50 percent inperson (n=180), and randomization will be stratified by site and format; the study is well-powered to detect differences in intervention effectiveness by format.

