5.6 Randomization and Stratification

Randomization of participants to study arms will be performed through the EDC system's enrollment module. The study arm assignments will be generated by the statistician at the SDMC. The SC Research Coordinator or designee will complete an eCRF in the EDC system to verify participant eligibility. Upon completion of the randomization, relevant SC staff will receive immediate notification of the study arm assignment on the randomization screen in the EDC system, followed by email notification. The relevant SC staff will maintain records of the participant's study arm assignment in accordance with the ATN MOGO.

Participants will be allocated with a 2:1 representation to the two arms, with two-thirds randomized to the IMPACT intervention and one-third to eSOC group. Block randomization will be stratified by SC and intervention format (online vs. in-person) to ensure balanced representation in the two arms. This allocation ratio was chosen to ensure sufficient power to examine whether there are differences in intervention efficacy by delivery format. Participants will be randomized after completing the Enrollment Visit and the first two RR sessions.

A randomization assignment, once issued, will not be re-allocated. Details of the randomization process are described in the study-specific Randomization Plan.

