14.2 Sample Size Considerations

Careful consideration was given to the effect size used in the power analysis and is estimated based on data from previous studies. In our pilot study, the mean difference in CAS acts between the intervention versus control arm at 6 months was 4.7 (>50% reduction). Although the pilot study had a large effect on reductions in sexual risk behaviors, effect sizes from small studies like the pilot study are less reliable and frequently inflated.^[70] Additionally, in the present study, the eSOC comparison group will be receiving two RR sessions and, as such, they will likely also decrease their engagement in CAS. Therefore, the study is powered to detect a 20 percent (or greater) reduction in the number of CAS acts between groups in the 12-month follow-up period, expecting both groups to show improvements from baseline. This decision will account for the fact that in clinical trials in general, and HIV behavioral trials in particular, when the control group receives any of the intervention content, it is more difficult to find a between-group difference^[71-73] as well as take into account the fact that the primary timeframe in the present study is 12 months instead of 6. Lastly, a 20 percent or greater reduction in the number of CAS acts has been previously described as a clinically meaningful change related to HIV sexual risk outcomes.

Moreover, to ensure sufficient power to assess whether intervention effectiveness differs between intervention delivery format (i.e., virtual vs. in-person) with a power of 90 percent, alpha level of 0.05, 291 participants will need to complete the proposed intervention in order to examine difference between IMPACT (n=194) and eSOC control (n=97). We plan to randomize 360 participants (n=240 in IMPACT and n=120 in eSOC) to account for 20 percent attrition at the month 12 visit.

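### The 90% power claimed for a difference by delivery format is supported only by figures for IMPACT versus eSOC

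*Protocol*

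**What the plan says.** Effectiveness by delivery format is the protocol's secondary objective (Section 2.1.3: "To determine the effectiveness of IMPACT by format of intervention (in-person vs. virtual"), with a matching endpoint in 2.2.3 ("Distinct acts of CAS by intervention format"). Three places speak to power for it.

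- **Section 14.2** says the sample is meant "to ensure sufficient power to assess whether intervention effectiveness differs between intervention delivery format (i.e., virtual vs. in-person) with a power of 90 percent" at alpha 0.05. The same sentence continues: "291 participants will need to complete the proposed intervention in order to examine difference between IMPACT (n=194) and eSOC control (n=97". The only design effect in the section is between arms: "the study is powered to detect a 20 percent (or greater) reduction in the number of CAS acts between groups". The pilot's larger reduction is also an arm contrast, and the section sets it aside as probably inflated.
- **Section 3** plans an even split ("We anticipate that about 50 percent of the randomized sample will participate virtually (n=180) and 50 percent inperson (n=180") and adds that "the study is well-powered to detect differences in intervention effectiveness by format".
- **Section 5.6**, on the 2:1 ratio: "This allocation ratio was chosen to ensure sufficient power to examine whether there are differences in intervention efficacy by delivery format".

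Section 14.3.4 commits to Poisson models for the format endpoints but leaves the model with an intervention-by-format interaction optional. Section 14.3.3 makes interaction models definite for geography, HIV status and race/ethnicity.

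**The concern.** Whether effectiveness differs by format is an arm-by-format interaction. The numbers in the sentence that claims 90% power for it are an arm comparison, as is the 20% effect. The protocol gives no format-difference size, no completer numbers by format and no format-specific rates, so nothing supports the format claim.

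The formats, the stratification, an objective and its endpoints, and the allocation ratio are all tied to this question. A reader told that the study is well powered for it could take a non-significant interaction as evidence that the formats work equally well. Yet the document does not show whether a 20% format difference would be found with 90% power or with less than half of that.

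**Working it through.** **Inputs.** From 14.2: 291 completers (194 and 97), 90% power, alpha 0.05, 20% reduction (rate ratio 0.80). From 14.3.1: two-sided tests. From Section 3: 50:50 format split. Completers per cell are therefore 97 per format on IMPACT and 48.5 per format on eSOC. No rate, dispersion or within-person correlation is given, so the power figures below are conditional.

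**Can 291 be reproduced?** Not directly. Solving backwards, 194 versus 97 gives 90% power for an arm contrast at a standardized difference of 3.2415 × √(1/194 + 1/97) = 0.403. Entering an assumed 0.40 gives 297, which is close to 291 but does not show how 291 was obtained.

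**Relative precision**, equal variance on the log scale (per-person variance cancels):
- Arm contrast: 1/194 + 1/97 = 0.01546.
- Interaction: 2/97 + 2/48.5 = 0.06186.
- Variance ratio 4.0, so the standard error doubles.

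Poisson check (a common factor, dispersion over control mean, cancels):
- Arm: 1/(0.8 × 194) + 1/97 = 0.01675.
- Interaction, rate ratio 0.80 in both formats: 2/(0.8 × 97) + 2/48.5 = 0.06701, which is 4.00 times the arm variance.
- Interaction, rate ratios 1.00 and 0.80: 1/97 + 1/(0.8 × 97) + 2/48.5 = 0.06443, which is 3.85 times.

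**Power under two readings of 291.** Effect |ln 0.80| = 0.2231; z = 1.960 + 1.2816 = 3.2415.

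| | 291 sized for arms at 0.80 | 291 sized for interaction at 0.80 |
|---|---|---|
| Arm power at 0.80 | 90% | Φ(2 × 3.2415 − 1.96): over 99.9% |
| Interaction power at 0.80 | Φ(3.2415/2 − 1.96): 37% | 90% |
| Interaction detectable at 90% | exp(−2 × 0.2231) = 0.64 | 0.80 |
| Control mean ÷ dispersion required (Poisson, 0.80 in both formats) | 0.01675 × 3.2415² / 0.2231² ≈ 3.5 | 0.06701 × 3.2415² / 0.2231² ≈ 14.1 |

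In the left column, the Poisson case with rate ratios 1.00 and 0.80 gives 38% instead of 37% and a detectable ratio of about 0.65. Reaching 90% at 0.80 for the interaction would take about 4 × 291 = 1,164 completers. The document fixes neither value in the last row, so it does not choose between the columns.

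**Does 2:1 serve the format question?** Variance at 2:1 relative to 1:1, both with 291 completers (72.75 per cell at 1:1):
- Interaction, equal log-scale variance: 0.06186 / (4/72.75) = 1.125.
- Interaction, Poisson, 0.80 in both formats: 1.083.
- Interaction, Poisson, 1.00 and 0.80: 1.103.
- Virtual versus in-person within IMPACT only: (2/97) / (2/72.75) = 0.75.

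So 2:1 costs the interaction 8.3% to 12.5% in variance. It helps only a within-IMPACT comparison, which does not use the control arm and so does not measure effectiveness against eSOC.

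**The case against.** The strongest reply is that 14.2 attaches 90% only once, to format, and puts no power figure on the 20% arm effect. If format is the more demanding requirement and set 291, the arm comparison has more than enough power and the two statements do not conflict. That reading is possible and is the right-hand column above. It still lacks its essential input, the size of the format difference, and it sits badly with a sentence that describes 291 as an IMPACT versus eSOC comparison. The objection is right that 37% is one conditional case and not the trial's established power.

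It can also be said that a format result would be read from its confidence interval whatever power was planned, that the 2:1 penalty is small (4% to 6% in standard error), and that 2:1 helps format comparisons within IMPACT, such as fidelity. All of that is fair. The 2:1 cost is minor; the objection to Section 5.6 is that the reason it gives does not hold for the interaction.

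Finally, details of a secondary model can be left to the SAP. But the protocol itself asserts 90% power for this question, and it is less definite about the test that answers it than about interactions with supplementary factors.

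**Conclusion.** The concern holds. The 90% format claim in 14.2, and its repetition in Section 3, are unsupported: the effect size and counts beside them belong to the arm contrast, and no format effect is stated. Exactly 90% cannot apply to both contrasts at the same effect size, because their standard errors differ by a factor of two under a 50:50 split and equal dispersion. Interaction power at a ratio of 0.80 is about 37% if 291 was sized at 90% for the arms, and 90% if it was sized for the interaction; the protocol does not let a reader choose. The 2:1 rationale in 5.6 is wrong for the interaction, by a modest amount. The primary hypothesis and its estimand are not affected. This should be fixed, but it does not threaten the main result.

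**What to change.** - **14.2:** say which contrast 291 and 90% refer to, with the sponsor's own rate and dispersion assumptions. Then either state the ratio of rate ratios detectable at 90% on those assumptions or withdraw the 90% format claim. If 291 was sized for the interaction, say so and give the resulting arm power.
- **Section 3:** bring the statement about format power into line with that result.
- **5.6:** say which format comparison the 2:1 ratio serves, and that it does not improve power for the arm-by-format interaction.
- **14.3.4:** make the intervention-by-format interaction a definite analysis, reported with its 95% confidence interval.

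The cost is text only, with no added participants. The stated power for the format question may become less favourable.

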14.3 Statistical Analysis Methods

14.3.1 General Analysis Considerations

All data collected will be summarized and/or listed. Analyses will be performed using SAS[®] software (SAS Institute Inc., Cary, NC) version 9.4 or higher.

Unless otherwise specified, descriptive statistics include the mean, SD, median, minimum, maximum for continuous variables, and the number and proportion in each group for categorical variables. Unless otherwise specified here or in the SAP, statistical tests and confidence intervals (Cis) will be computed using a two-sided 5 percent significance level. Exact Cis will be used for univariate summaries of dichotomous variables, and Wald- or score-based Cis will be used for mean/rate differences/ratios. All proportions will use as denominator the number of subjects contributing data at the specified time point within the specified group and analysis population. Summaries will be presented by intervention and by time point, where relevant.

For all summaries outlined in this section, the SAP will contain additional detailed descriptions of the analyses to be conducted.

14.3.2 Populations for Analyses

Intent-to-Treat Population

Analyses of primary and secondary endpoints will be conducted in an Intent-to-Treat population that includes all randomization participants. Participants will be analyzed according to the intervention to which they were randomized.

14.3.3 Analysis of Primary Endpoint

Estimands

The primary analysis of the primary endpoint will compare the rate of distinct acts of CAS over the course of follow-up between the IMPACT intervention arm and the eSOC comparison arm.

For this endpoint, the primary estimand is defined by the following attributes:

- **Intervention condition:** IMPACT intervention versus eSOC including the effects of intervention discontinuation and intake of additional interventions/therapies.
- **Population:** Cisgender YGBSMM as defined by the inclusion criteria to reflect the key population.
- Variable: Number of distinct acts of CAS without the use of a condom or without the protection of prevention-effective PrEP (for participants NLWHIV) or viral suppression (for participants LWHIV) over the course of follow-up.
- Intercurrent events: The following intercurrent events are anticipated:

- Discontinuation of intervention due to any reason
 - Handling strategy: treatment policy (captured through the intervention condition definition)
- Intake of additional interventions/therapies
 - Handling strategy: treatment policy (captured through the intervention condition definition)

Further intercurrent events are not anticipated at this time.

• **Population-level summary:** Rate ratio between intervention conditions

Analysis Models

For the primary endpoint, a marginal Poisson model will be used, with logarithmic link function, common intercept, linear fixed effect for intervention, and accounting for the length of the reporting period for each observation. A Generalized Estimating Equations (GEE) approach will be used to fit the model, assuming an unstructured working correlation structure. Given the possibility of missing data from participants who discontinue the study prior to the Month 12 visit, inverse probability weighting will be incorporated into the modeling procedure; more details will be described in the SAP. Substitute model specifications to be used in the event the primary model does not converge will be described in the SAP.

Least squares means will be used to estimate intervention-specific rates; the rate point estimates and standard errors will be reported. The intervention comparison will use the rate ratio comparing IMPACT to eSOC, which will be estimated along with its 95 percent CI from the model. The primary hypotheses will be tested via the Type 3 likelihood ratio chi-square test of the intervention fixed effect. The test statistic value and p-value will be reported.

Supplemental and Sensitivity Analyses

Primary model estimates and results will be accompanied by tabulated summary statistics of the endpoint data by intervention and visit. The primary model will also be used to assess the treatment effect at the Month 4 and Month 8 time points by incorporating a covariate for time point using appropriate contrasts.

Additional models that add a linear effect for a baseline/demographic factor as well as an (intervention * factor) interaction term will be used to assess the effect of intervention by factor. The factors that will be investigated (in separate models) will include geography, HIV status, and race/ethnicity.

Sensitivity analyses will also be performed for the primary endpoint. The SAP will describe the analyses in more detail.

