1.2.2.3 NIDA-Funded Pilot RCT of the IMPACT Intervention

In this pilot RCT, 41 participants NLWHIV (21 intervention, 20 control) were randomized across the two study arms: (1) BA-RR (BA and RR counseling), which lasted 10 sessions, and (2) the eSOC comparison arm, which included 2 equivalent RR counseling sessions without any additional intervention.^[13] Participants were followed for 6 months. Main outcomes included the number of CAS acts without protection of PrEP and the number of stimulant use episodes. At

baseline, in the prior month, participants had an average of 11 sexual partners, had CAS 18 times on average, and had CAS while using stimulants 16 times on average. In longitudinal Poisson regression models, the main sexual risk outcome data showed fewer CAS acts overall between the intervention and comparison arm (p<0.0001). Similarly, fewer CAS acts were demonstrated while using stimulants (2.24 [0.2] vs. 6.94 [0.4] p<0.0001) and fewer CAS acts with a serodiscordant partner while using stimulants (1.0 [0.2] vs. 2.5 [0.4] p=0.0005), both at 6-month follow-up. Also, at 6-month follow-up, the intervention group reported a longer period of stimulant non-use in the past 90 days (50.10 [1.5] vs. 39.00 [1.4] p<0.0001] vs. standard of care (SOC)).

1.2.2.4 National Institute of Allergy and Infectious Diseases/Centers for AIDS Research Funded Pilot of IMPACT Intervention for MSM with HIV

An open pilot trial of the IMPACT intervention (approximately 10 BA sessions) was conducted for MSM with stimulant use disorder who were LWHIV (n=11).^[12] This study provides preliminary evidence that the intervention for this population was feasible (100% retention at 6 months) and acceptable (100% of intervention sessions attended). Exit interviews indicated that the intervention was well received and acceptable. The mean change score in self-reported stimulant use within the past 30 days (within-person change; reduction in self-reported stimulant use) was 4.14 days at 3 months and 5.0 days at 6 months (Cohen's d=0.89). The mean change score in weekly toxicology screens (reduction in positive toxicology screens) was .71 at 3 months and 1.0 at 6 months (Cohen's d=1.05).

2. **Objectives and Endpoints**

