7.5 Efficacy Assessments

All study assessments are listed in Appendix 2. In brief, primary efficacy will be determined by a combination of self-report and biomarkers at each follow-up visit. Participants will be asked to report the number of times (continuous) in the past 4 months they have engaged in CAS with a male partner. Those who report oral PrEP use will also provide blood samples for assessing PrEP adherence, and those who report injectable PrEP use will be asked to provide a medical record release to confirm receipt of their bimonthly injections. Similarly, those who are LWHIV will provide blood samples for viral load testing.

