8.3 Pharmacology

DBS samples for pharmacology testing will be collected throughout the study from both inperson and virtual participants; however, this testing may be limited to a subset of samples. For participants reporting long-acting PrEP, plasma may be used to assess drug concentrations. Procedures for sample processing and shipping are outlined in the study Lab Processing Chart (LPC). The primary pharmacologic assessments will be performed using assays that have been appropriated validated and approved by the Central Laboratory, an external quality assurance group. Interpretation of pharmacologic results, including modeling, will be led by the Central Laboratory and the ATN Laboratory Diagnostics and Mobile Technologies Scientific Leadership Group, in collaboration with other groups, as needed.

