Additional information may need to be gathered to evaluate SAEs and to complete the appropriate eCRFs and the summary. This process may include obtaining hospital discharge reports, medical records, autopsy records and/or any other type records or information necessary to provide a complete and clear picture of the SAE and events preceding and following the event. If the SAE is not resolved or stable at the time of the initial report or if new information becomes available after the initial report, follow-up information must be submitted as soon as possible.

Like AEs, each SAE must be followed until the event has resolved, returned to baseline, or has been deemed stable and is not expected to worsen, based on the judgment of the SC Project Lead. If the event resolves during the study or follow-up period, a resolution date should be documented.

14. Statistical Considerations

This section summarizes the primary features of the statistical analysis for the study. A statistical analysis plan (SAP) will be prepared and finalized prior to database lock and will specify all analyses to be performed. Major changes in the analysis (e.g., redefinition of analysis methodology of a primary endpoint) should result in a protocol amendment. Minor changes, deviations, or changes from the statistical analyses specified in the protocol will be described and justified in the SAP and/or the final study report.

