14.7 Missing, Unused, and Spurious Data

As noted in Section 14.3.3, missing primary endpoint data will be handled via inverse probability weighting. The use of weighted GEE provides estimates that are consistent with data that are Missing at Random (MAR). Sensitivity analyses will address missing primary endpoint data in multiple ways: (1) ignoring missing data, which assumes the data are Missing Completely at Random (MCAR), and (2) imputing using multiple imputation, which provides consistent estimates when missing data are MAR.

Missing implementation endpoint, safety, and participant characteristic data will be assumed to be MCAR, and no imputation will be performed.

Planned explorations of outlying or influential data will be described in the SAP.

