15.1.2 Known Potential Risks and Benefits to Human Participants

15.1.2.1 Known Potential Risks

- Finger Prick: Participant may feel minor pain from pricking their finger. It is less likely that the participant could bruise where they prick their finger. It is rare that the participant would get an infection where they prick their finger.
- Blood drawing: It is possible that the participant may feel discomfort during the blood draw. It is also possible there may be bruising, swelling, or bleeding where the needle

enters the skin. The participant may also feel dizzy or light-headed when blood is drawn. The total participant blood volume drawn will not exceed the maximum blood volume allowed for the study period.

- Discomfort with survey questions: All participants will be informed that they can decline to answer any question that makes them uncomfortable without consequence. They will also be reminded that all their responses are confidential.
- Potential risk of loss of confidentiality: There is a potential risk of loss of confidentiality. Every effort will be made to protect the participant's confidential medical information, but this cannot be guaranteed.
- Unforeseen risks: There may be other risks to the participant in this research that are not known or foreseeable at this time.

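### The primary Poisson model does not use the CAS count collected at enrollment, before randomisation: the rate ratio stays valid, but precision may be given up, by an amount the protocol does not let one fix

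*Protocol*

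**What the plan says.** Section 14.3.3 compares CAS rates over follow-up. It describes the mean model as one "with logarithmic link function, common intercept, linear fixed effect for intervention, and accounting for the length of the reporting period for each observation". Inverse probability weights handle dropout. Arm rates come from least squares means, and the intervention effect is tested with a Type 3 likelihood ratio test. Additional models bring in geography, HIV status and race/ethnicity, but not enrollment CAS. Section 14.3.4 applies the same procedures to the key secondary endpoint.

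On measurement, Section 7.5 has participants "report the number of times (continuous) in the past 4 months they have engaged in CAS with a male partner" at each follow-up visit. Section 3 schedules a self-reported sexual risk battery at enrollment and at Months 4, 8 and 12, and Appendix 2 marks the Sexual Behavior and Sexual Risk questionnaires at enrollment and at each of those visits. Section 3.2.4 places randomisation after the Enrollment Visit and after two risk-reduction sessions that everyone receives. Section 5.6 stratifies randomisation by Site Consortium (SC) and format.

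On changes to the plan, the opening of Section 14 says: "Major changes in the analysis (e.g., redefinition of analysis methodology of a primary endpoint) should result in a protocol amendment". It lets minor changes go into the SAP or the final report.

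**The concern.** A count of the same behaviour, recorded before randomisation, is often the strongest predictor of the follow-up count. It cannot be affected by arm and it is already being collected. The mean model leaves it out, and because the outcome covers follow-up only, it is not an outcome record either.

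If enrollment CAS predicts follow-up CAS, adjusting for it narrows the confidence interval around the 20% reduction for which the trial is powered. If it does not, little is lost. At stake is the width of the interval for the primary and key secondary comparisons, not the correctness of the estimate.

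**Working it through.** **1. The plan's own figure.** Section 14.2 gives 291 completers (194 IMPACT, 97 eSOC), 90% power, alpha 0.05 and a 20% reduction. It gives no CAS rate, dispersion or correlation, so 291 cannot be reproduced forwards.
- Attrition: 291/0.80 = 364, against 360 stated (360 × 0.80 = 288), which is close enough.
- Solving backwards, reading 291 as the number for the arm comparison: required SE of the log rate ratio = |ln 0.80|/(1.960 + 1.282) = 0.223/3.242 = 0.0688. The implied coefficient of variation of the per-person rate is 0.0688/√(1/97 + 1/194) = 0.0688/0.1244 ≈ 0.554. The protocol does not state this value.

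**2. Approximation.** Adjustment multiplies the variance by 1 − r², where r is the correlation of enrollment with follow-up CAS. The equivalent number randomised is 360/(1 − r²).

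| Assumed r | Variance cut | Equivalent randomised |
|---|---|---|
| 0 | 0% | 360 |
| 0.3 | 9% | 396 |
| 0.5 | 25% | 480 |

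If the unadjusted design truly has 90% power, r = 0.3 gives 92.5% and r = 0.5 gives 96.3%.

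**3. Simple simulation.** Complete data, 194 against 97, overdispersed Poisson counts summed over three visits, true rate ratio 0.80, 400 runs per setting. The average rate ratio was 0.798 to 0.810 both with and without enrollment CAS, so leaving it out causes no bias. Adjusted/unadjusted variance ratios were 1.00 to 1.01 at correlation 0, 0.92 to 0.96 at about 0.28, 0.88 at 0.43 and 0.71 at 0.48.

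**4. Fuller simulation.** 360 randomised 2:1 within 10 SC-by-format cells, three visits, dropout of about 7/15/22% at Months 4/8/12, inverse probability weights, unstructured working correlation and a small-sample-corrected sandwich SE. The covariate is log(self-reported baseline + 1), with 5% of baselines missing and imputed with an indicator. SC and format enter as main effects. The anchors come from the pilot trial in Section 1.2.2.3, whose participants "had CAS 18 times on average, and had CAS while using stimulants 16 times on average" in the month before baseline and whose control arm averaged 6.94 stimulant-related acts at 6 months. Dispersion, correlation, dropout, site effects and the share of protected acts are assumed.

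Moderate dispersion, 3,000 runs per setting:

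| Realised r | Variance change (95% Monte Carlo interval for the cut) | Equivalent randomised, 360/(1 − cut) |
|---|---|---|
| 0.03 | rise 2.7% (−4.8 to −0.9) | 351 |
| 0.19 | cut 4.0% (1.4 to 6.5) | 375 |
| 0.31 | cut 10.0% (7.0 to 12.4) | 400 |
| 0.39 | cut 21.8% (18.8 to 24.6) | 460 |

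At high dispersion (2,000 runs per setting) the cut was 1.8% (−3.4 to 6.3) at r 0.02 and 20.3% (15.3 to 25.3) at r 0.34. At r 0.31 and moderate dispersion, the unadjusted and adjusted rate ratios were 0.807 and 0.805, coverage was 94.2% and 94.8%, and rejection under the null was 5.8% and 5.0%.

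Entering SC and format alone changed the variance by a rise of 1.4%, a cut of 1.3%, and rises of 0.2% and 0.2% over the same four settings. That is effectively nothing, so the gain comes from enrollment CAS.

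**5. What adjustment brings with it.**
- *Missing baselines.* Dropping the 5% with no baseline (18 of 360) instead of imputing turns the four results into a rise of 7.9%, a rise of 1.2%, a cut of 5.5% and a cut of 17.2%. About half the gain at r 0.31 goes, and all of it at r 0.19.
- *Arm rates.* Default least squares means of the adjusted model were 5.87 and 4.71 acts, against 6.56 and 5.26 standardised over the observed covariates. 5.87/6.56 = 0.895, about 10.5% low. The present unadjusted model does not have this problem (6.53 and 5.25).
- *Choice of covariate.* A baseline built like the endpoint, with protected acts removed, would change the four results to a rise of 1.6% and cuts of 9.5, 16.1 and 26.7%. It may not be available for everyone, because Section 8.3 says of the drug-concentration assays: "however, this testing may be limited to a subset of samples".

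**The case against.** The strongest reply is that nothing here is wrong. An unadjusted marginal model matches the declared estimand, and adjustment is a preference. The first half stands: this is an efficiency point. But a specific value already in the data is left unused in a model the protocol spells out, and using it costs little.

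The second reply is that the gain rests on a correlation nobody has stated, and the design may lower it. Two risk-reduction sessions fall between the measurement and randomisation, eligibility requires recent stimulant-related CAS, and the endpoint removes protected acts that the self-reported count includes. This stands. At r 0.31 the interval narrows by about 5% (√0.90 = 0.949); at r 0.19 by about 2% (√0.96 = 0.980).

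The simulation has real limits. The pilot anchors are stimulant-related acts in HIV-negative men, and the baseline one covers one month rather than four. The covariate's log form suits the way the data were generated. Unstable fits were set aside (4 to 13 of 3,000 at moderate dispersion, 25 and 31 of 2,000 at high). The coverage and rejection figures use a sandwich SE, not the likelihood ratio test in Section 14.3.3. Direction is better supported than size.

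The unseen SAP might use enrollment CAS in the dropout weights and recover some precision. That would not change the stated mean model.

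Four stronger readings are tempting, and the documents do not support them:
- *The primary estimate is biased.* Randomisation protects it, subject to the weights and the missing-at-random assumption in Section 14.7. Section 14.1 words the hypothesis as a reduction from baseline, but its null and alternative compare rates between arms, which is what the model does.
- *The trial is underpowered without the covariate.* Section 14.2 gives no dispersion, so this cannot be shown.
- *Omitting SC and format costs precision.* The simulation shows no measurable loss.
- *Section 14 requires an amendment for this change.* It reserves amendment for major changes, and one added covariate with the same endpoint, link, weights and rate ratio can be read as minor.

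**Conclusion.** The point holds as one of precision only. The primary model, and through Section 14.3.4 the key secondary model, make no use of an enrollment value collected before randomisation. Under assumed correlations from 0 to about 0.4, adjusting would change the variance of the log rate ratio by anything from a rise of about 3% to a cut of about 20%, with a cut of roughly 10% near 0.3. Where this trial lies in that range cannot be read from the protocol.

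The estimand is kept: with a log link and no treatment-by-baseline interaction, the adjusted and unadjusted rate ratios target the same quantity. The change is worth making because the likely downside is small and the possible gain several times larger. Confidence is medium, since every figure for the gain rests on assumed inputs.

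**What to change.** Prespecify log(self-reported enrollment CAS count + 1) as a covariate in the primary model, either in Section 14.3.3 or in the SAP before outcome data are seen. Keep the log link, the reporting-period offset, the inverse probability weights and the rate ratio. In addition:

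- **Test.** Replace the Type 3 likelihood ratio test with a Wald or score test based on a robust variance, with a small-sample correction.
- **Missing baseline.** State an arm-blind rule, for example imputing the overall baseline mean with a missing indicator. It is needed because Section 15.1.2.1 tells participants that "they can decline to answer any question that makes them uncomfortable without consequence", while the Intent-to-Treat population "includes all randomization participants". Write it as an explicit exception to Section 14.7, which says: "Missing implementation endpoint, safety, and participant characteristic data will be assumed to be MCAR, and no imputation will be performed".
- **Arm rates.** Report rates standardised over the observed covariates instead of default least squares means.
- **Sensitivity analysis.** Keep the unadjusted model.
- **Key secondary endpoint.** Do the same with enrollment stimulant use, which Appendix 2 also schedules.
- **SC and format.** Entering them is optional and only reflects the stratified design; no precision gain is claimed. If they are entered, use main effects with small SCs pooled: a full cross of five SCs and two formats would average 120/10 = 12 eSOC participants per cell.

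The cost is a change of wording and somewhat more analysis work, with no new data collection. Standardised rates and a missing-baseline rule become necessary, which the present model does not need. If enrollment CAS predicts follow-up poorly, there is no gain, or a loss of about 3%.
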